2.2 Secondary Objectives

2.2.1 To determine impact of PRO monitoring with symptom alerts compared to PRO monitoring without symptom alerts after thoracic surgery on post-operative readmission and mortality rates by analyzing:

1. 30-day post-discharge emergency department visit rate
2. 90-day post-discharge emergency department visit rate
3. 30-day post-discharge readmissions rate
4. 90-day post-discharge readmissions rate
5. 30-day mortality (percentage)
6. 365-day mortality (percentage)
7. Change in 2-year quality of life

2.2.2 To determine feasibility of PRO monitoring after thoracic surgery in regards to monitoring long-term quality of life. Feasibility is defined as $\geq 50\%$ of patients completing all quality of life surveys at baseline and all follow-up time points.

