4.3 Study Details

Participants complete electronic surveys to assess their baseline and post-operative characteristics, symptoms, quality of life, and health outcomes. The study consists of a total number of 9 different surveys.

Figure 2: Survey Frequency and Duration

Survey	Frequency	Completion Time
Pre-operative Symptom Survey	1	5 minutes
Patient Demographics	1	3 minutes
PROMIS Physical Function SF 4a Survey	32	2 minutes
EORTC QLQ-LC13 survey	8	3 minutes
EORTC QLQ-C30 survey	8	8 minutes
Patient Satisfaction survey	7	3 minutes
Readmission Patient Survey	7	2 minutes
Post-operative symptom Daily Survey	15	7 minutes
Post-operative symptom Weekly Survey	11	7 minutes

Enrollment/Baseline Visit

Patients at the multidisciplinary thoracic oncology clinic with plans for thoracic surgery will be approached for enrollment based on inclusion/exclusion criteria described above. An IRB-approved study team member will approach the patient to discuss study procedures, benefits, risks and obtain informed consent prior to any study procedures. The study team member will also teach the patient how to complete the PRO assessment using PRO Core.

At that time, the participant will complete their pre-operative PRO assessment in a private area, which will include PRO surveys as well as demographic questions such as age, sex, and education. PRO survey responses will be reported using the PRO Core database. Paper copies of PRO surveys and source documents will be used if PRO Core system is inaccessible.

For patients who are found to be ineligible during screening or those potentially eligible during screening but found to be ineligible after contact, reasons for ineligibility as well as basic demographics available in the EMR (e.g. race, ethnicity, age, gender, education level if available) will be collected in PRO Core.

For patients who are eligible but refuse enrollment, reasons for refusal, as well as basic demographics available in the EMR (e.g. race, ethnicity, age, gender, education level if available) will also be collected within PRO Core.

Discharge Day (Day 0) Visit:

On the day of discharge (or the next business day in the case of late or weekend discharges), discharge day surveys will be activated in PRO Core by the study staff.

A study team member will call or approach participant in their hospital room before or after discharge to reorient the participant with PRO Core, if needed.

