Participants will be reminded of the post-discharge survey schedule, helped with any questions they may have, and assisted with completing any due surveys, if needed.

In the case the day of discharge survey is not obtained (e.g late in the day discharges, weekend discharges, and patient unable or unwilling to complete a survey), this will not be considered a protocol deviation.

The study team member activating the discharge day survey will obtain surgical information from Epic, the surgeon or surgery care team member.

Day 0 (Discharge) to Day 14 Post-Discharge

At this time the following procedures will be performed:

- Daily Post-operative symptom survey
- Daily PROMIS Physical Function SF 4a survey

Day 14 (+/- 7 days) Post-Discharge

At this time the following procedures will be performed:

- EORTC QLQ-LC13 survey
- EORTC QLQ-C30 survey
- Patient Satisfaction survey
- Readmission Patient Survey

Day 15 to Day 90 Post Discharge

Weekly symptom monitoring commences. At this time the following procedures will be performed:

- Weekly Post-operative symptom survey
- Weekly PROMIS Physical Function SF 4a survey

Day 60 Post-Discharge (+60 days)

At this time the following procedures will be performed:

- EORTC QLQ-LC13 survey
- EORTC QLQ-C30 survey
- Patient Satisfaction survey
- Readmission Patient Survey

Day 120 Post-Discharge (+60 days)

At this time the following procedures will be performed:

- EORTC QLQ-LC13 survey
- EORTC QLQ-C30 survey
- PROMIS Physical Function SF 4a survey
- Patient Satisfaction survey
- Readmission Patient Survey

Day 180 Post-Discharge (+185 days)

At this time the following procedures will be performed:

- EORTC QLQ-LC13 survey
- EORTC QLQ-C30 survey
- PROMIS Physical Function SF 4a survey
- Patient Satisfaction survey
- Readmission Patient Survey

Day 365 Post-Discharge (+180 days)

At this time the following procedures will be performed:

- EORTC QLQ-LC13 survey
- EORTC QLQ-C30 survey
- PROMIS Physical Function SF 4a survey
- Patient Satisfaction survey

Day 545 Post-Discharge (+185 days)

At this time the following procedures will be performed:

- EORTC QLQ-LC13 survey
- EORTC QLQ-C30 survey
- PROMIS Physical Function SF 4a survey
- Patient Satisfaction survey

Day 730 Post-Discharge (+185 days)

At this time the following procedures will be performed:

- EORTC QLQ-LC13 survey
- EORTC QLQ-C30 survey
- PROMIS Physical Function SF 4a survey
- Patient Satisfaction survey

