7.0 STATISTICAL CONSIDERATIONS

7.1 Study Design

This is a single center, randomized feasibility study. A total of 140 patients undergoing thoracic surgery will be prospectively enrolled and randomized in a 1:1 ratio. A random block method with blocks of 20 will be utilized to randomize participants to one of two arms to complete PRO (patient reported outcome) symptom monitoring. The two arms are 1) active symptom monitoring and 2) passive symptom monitoring. The participants randomized to active symptom monitoring will have alerts sent to their clinicians when their PRO symptom scores exceed baselines scores by 2 points or more, or when 'severe' or 'very severe' symptoms are reported. Participants randomized to the passive PRO monitoring arm will complete the same PROs as participants in the active monitoring arm, but will not have alerts sent to their clinician. All participants will be administered survey instruments to further assess quality of life including: EORTC QLQ30, EORTC LC13, PROMIS Physical Function SF 4a survey SF 4a. Additionally, in order to assess the feasibility of the PRO monitoring system, all participants will be asked to complete a Patient Satisfaction survey. In addition, a subset of 40 participants and 40 caregivers will be chosen to complete a semi-structured interview, if willing, to assess patient satisfaction with symptom monitoring experience. The subset will be made up of a range of post-operative experiences and will be a fair representation of study population, including both

study arms. Participants will be chosen by principal investigator and eligible to participate in interview after 14 days of discharge

The primary objectives are to determine 1) impact of PRO monitoring with symptom alerts compared to PRO monitoring without symptom alerts after thoracic surgery on post-operative quality of life 2) feasibility of 3-month post-operative PRO symptom monitoring after thoracic surgery symptom monitoring eliciting a clinician response 3) barriers/facilitators of PRO monitoring after thoracic surgery through semi-structured interviews of patients.

Secondary objectives include: 1) determining impact of PRO monitoring with symptom alerts compared to PRO monitoring without symptom alerts after thoracic surgery on post-operative readmission and mortality rates 2) determining feasibility of PRO monitoring after thoracic surgery in regards to monitoring quality of life.

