7.3 Data Analysis Plans

7.3.1 Aim 1: Impact of PRO monitoring with symptom alerts, compared to PRO monitoring without alerts, after thoracic surgery on post-operative quality of life.

Impact will be determined by comparing baseline quality of life to quality of life at the following timepoints: Day 14, Day 60, Day 120, Day 180, and Day 365 post-discharge. QOL will be measured by administering European Organisation for Research and Treatment of Cancer's (EORTC) EORTC QLQ-LC13 and EORTC QLQ-C30. These surveys will be scored according to methods described in the EORTC scoring manual: <https://qol.eortc.org/manual/scoring-manual>.

Student's T and/or Wilcoxon rank sum tests will be used to perform bivariable comparisons of EORTC scores at each of the time points (baseline/pre-operative and Day 12, Day 60, Day 120, Day 180, and Day 365 post-operative).

Additionally, a linear mixed effect model will be used to assess the average

change in EORTC scores over time amongst both groups, and the difference in average trajectory between them, after accounting for repeated measures and within- and between- subject variability. Both a random intercept and slope (for time) statement will be used, and an unstructured correlation matrix will be applied. The random intercept and slope will allow us to assess the impact of symptom alerts while allowing for random variation in baseline quality of life and trajectories.

If there are convergence issues, simpler correlation structures may be used (e.g. independent) or the random slope parameter may be dropped. Dropping the random slope parameter will mean we are assuming that there is no/minimal individual variation in trajectory across patients.

7.3.2 Aim 2: Determine feasibility of 3-month post-operative PRO symptom monitoring with alerts.

The proportion of completed symptom surveys (overall and in each arm) at 3-months postoperative will be calculated, as well as the proportion of participants who completed all surveys during that time. Chi-square, Student's T, and Wilcoxon rank sum tests will be used to compare patient demographics, study arm, and surgery characteristics between those who did and did not complete all surveys to attempt to identify predictors of compliance. Multivariable logistic regression may also be used.

Similar methods will be used to assess proportion of symptom alerts that generate a clinician response.

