7.3.3 Aim 3: Identify barriers/facilitators of PRO monitoring through semi-structured interviews.

Patient and caregiver interview transcripts will be analyzed as they are collected. Transcripts will be coded using in vivo coding methods and a code book will be created. Interviews will continue until thematic saturation is achieved, which will be defined by no new codes being generated to add to the code book.

7.3.4 Sub-Aim 1: Impact of PRO monitoring with symptom alerts, compared to PRO monitoring without symptom alerts, on post-operative readmission and mortality rates.

Kaplan Meier curves and Cox proportional hazards regression will be used to assess the impact of study treatment arm on 30-day and 90-day emergency department (ED) visits, readmissions, and all-cause mortality, as well as 1-year all-cause mortality. A linear mixed effect model will be used to assess the change in 2-year quality of life (described in Aim 1).

Patients who are lost to follow-up will be censored at their last clinician/study interaction. Mortality will be treated as a competing risk for ED visits and readmission. This aim will be approached as an intent-to-treat analysis and will not require that patients used their PRO monitoring or had symptom alerts sent to

their clinician.

7.3.5 Sub-Aim 2: Determine the feasibility of PRO monitoring for assessing quality of life.

Similar methods to Aim 2 will be used. The proportion of completed QOL surveys (overall and in each arm) at each time point (baseline/pre-operative and 2-weeks, 6-months, 1-year, and 2-year post-operative) will be calculated, as well as the proportion of participants who completed all surveys during that time. Chi-square, Student's T, and Wilcoxon rank sum tests will be used to compare patient demographics, study arm, and surgery characteristics between those who did and did not complete all surveys to attempt to identify predictors of compliance. Multivariable logistic regression may also be used.

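### Section 7.3.5 lists five of the eight scheduled EORTC time points for quality-of-life completion, so Days 60, 120 and 545 have no planned proportion and the 50% criterion of objective 2.2.2 can be misread as a five-visit test

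*Combined protocol and SAP*

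**What the plan says.** Objective 2.2.2 sets the criterion at 50% or more "of patients completing all quality of life surveys at baseline and all follow-up time points".

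Section 4.3 gives the schedule. Both EORTC forms (QLQ-C30 and QLQ-LC13) are due at seven post-discharge visits, among them "Day 545 Post-Discharge (+185 days" window). The table headed "Figure 2: Survey Frequency and Duration" gives a frequency of 8 for each form, which is the seven visits plus baseline.

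Section 7.3.5 is the analysis for objective 2.2.2. It promises a completion proportion for every time point, overall and by arm, and then names the time points as "baseline/pre-operative and 2-weeks, 6-months, 1-year, and 2-year post-operative) will be calculated". It goes on to the proportion of participants who completed every survey, using the same closing phrase as 7.3.2, where the plan reads "at 3-months postoperative will be calculated, as well as the proportion of participants who completed all surveys during that time". Section 7.3.5 does not mention the 50% threshold.

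Two other sections bear on the point. Section 7.3.1 compares QoL with baseline "at the following timepoints: Day 14, Day 60, Day 120, Day 180, and Day 365 post-discharge". Section 7.3.4 adds: "A linear mixed effect model will be used to assess the change in 2-year quality of life".

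**The concern.** The list in 7.3.5 is shorter than the schedule and shorter than the objective requires, and no reason is given for leaving visits out. Two things follow.

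First, a completion table built from 7.3.5 as written would be blank at three scheduled visits, although the section says it covers each one. A study meant to show whether QoL can be followed over two years needs to show where completion falls off.

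Second, the all-surveys proportion stands directly after the five-point list. An analyst could compute it over those five visits and set it against the 50% of objective 2.2.2. That would be an easier test than the objective states, and the choice could be made after the completion data are known.

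**Working it through.** **Count of scheduled points.** From section 4.3: baseline, then Days 14, 60, 120, 180, 365, 545 and 730 after discharge, so 1 + 7 = 8. This reproduces the 8 in Figure 2 for each EORTC form. The table in section 5.1 is not needed.

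**Comparison with 7.3.5.** Matching 2 weeks, 6 months, 1 year and 2 years to Days 14, 180, 365 and 730 is an inference, because 7.3.5 counts from surgery and 4.3 from discharge.

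| Scheduled point (4.3) | Named in 7.3.5 | By-day comparison in 7.3.1 |
|---|---|---|
| Baseline | yes | yes |
| Day 14 | yes | yes |
| Day 60 | no | yes |
| Day 120 | no | yes |
| Day 180 | yes | yes |
| Day 365 | yes | yes |
| Day 545 | no | no |
| Day 730 | yes | no |

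Five are named and 8 − 5 = 3 are omitted. Day 545 alone appears in neither list.

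**Direction of the difference.** Anyone who completes all eight visits has completed the five, so the eight-visit proportion cannot exceed the five-visit one. If missingness is purely monotone (once a visit is missed, all later ones are missed), everyone who completes Day 730 has completed every earlier visit and the two proportions are equal. They differ only when a patient completes all five named visits but skips Day 60, 120 or 545.

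**Size.** The documents give no completion rates, so the rates below are assumptions. The denominator is also assumed to be everyone enrolled: 140, or the lower figure of 100 from section 7.2. Let N be the denominator, T = 0.5 × N the number needed to pass, and C the number completing the five visits. The verdict changes from pass to fail when the number of those C who miss an added visit reaches C − T + 1.

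| N | T | C (share of N) | Misses that flip the verdict | Check |
|---|---|---|---|---|
| 140 | 70 | 77 (55%) | 77 − 70 + 1 = 8 | 77 − 8 = 69 |
| 140 | 70 | 84 (60%) | 84 − 70 + 1 = 15 | 84 − 15 = 69 (49.3%) |
| 140 | 70 | 112 (80%) | 112 − 70 + 1 = 43 | 112 − 43 = 69 |
| 100 | 50 | 55 (55%) | 55 − 50 + 1 = 6 | 55 − 6 = 49 |
| 100 | 50 | 60 (60%) | 60 − 50 + 1 = 11 | 60 − 11 = 49 |
| 100 | 50 | 80 (80%) | 80 − 50 + 1 = 31 | 80 − 31 = 49 |

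Below 50% on the five visits, both readings fail. The definition therefore matters mainly when five-visit completion is a little above the threshold: at 60% of 140, 15/84 = 17.9% of completers must skip an added visit, and at 80% it is 43/112 = 38.4%.

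**The case against.** The strongest reply is that the criterion is already fixed. Objective 2.2.2 requires every follow-up time point. Section 7.3.5 does not restate or change the threshold, and it says it follows the methods of Aim 2. In 7.3.2 the shared closing phrase refers to a period, so in 7.3.5 it most naturally means all surveys over the two years. This stands. A reader might infer that the plan has adopted a five-visit criterion; the documents do not support that, and the eight-visit reading is the better one. What remains is that the list contradicts the better reading, and the three missing proportions are missing on either reading.

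It can also be said that completion at Days 60 and 120 can be recovered from the numbers analysed in 7.3.1. That is right, and it leaves Day 545. A reader might infer that Day 545 is collected and never used, but it falls within the two-year model of 7.3.4; it lacks only a by-day comparison and a completion proportion.

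A reader might further infer that the PROMIS form counts toward the criterion, because section 7.1 says: "All participants will be administered survey instruments to further assess quality of life including: EORTC QLQ30, EORTC LC13, PROMIS Physical Function SF 4a survey". The documents point the other way. Section 7.3.1 measures QoL with the two EORTC forms, and the appendix list places only those two under the QoL heading, with PROMIS on its own line. Naming the forms in 7.3.5 is tidy, but this is not a separate fault.

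Finally, assumed rates just above 50% make a change of verdict look easy. That is fair, which is why the 80% case is shown beside them.

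**Conclusion.** The point holds as a minor one. The list in 7.3.5 is wrong against the schedule in 4.3 and the criterion in 2.2.2: it names five of eight points and omits Days 60, 120 and 545 without explanation. This rests on counting alone and is certain, apart from the inferred match between the labels in 7.3.5 and the study days.

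The effect on the 50% verdict is conditional. It needs an analyst to take the less natural five-visit reading, intermittent rather than monotone missingness, and five-visit completion not far above half. The counts of 15 of 84 and 43 of 112 rest on assumed rates and on all 140 enrolled as denominator, which the plan does not state.

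A reader might infer some damage to the QoL comparison between arms. There is none: this is a secondary feasibility measure, all eight administrations are collected in any case, and no efficacy test changes.

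**What to change.** In 7.3.5, replace the parenthesis with baseline/pre-operative and Days 14, 60, 120, 180, 365, 545 and 730 post-discharge. Say openly that this also moves the anchor from surgery to discharge, to match 4.3. Report completion at each of the eight points, overall and by arm. State that the proportion judged against 50% under objective 2.2.2 is taken over all eight points for the QLQ-C30 and QLQ-LC13.

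Name the denominator as well. Objective 2.2.2 says only patients, and over two years it matters how deaths are counted (365-day mortality is itself an endpoint), and how patients are counted whose surgery does not take place within three months of consent (exclusion 3.2.1).

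The cost is a wording change with no new data. The downside is a harder bar than the five-visit reading would set. The change should be dated and made before completion is tabulated.

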7.4 Data Management/Audit

PRO data will be collected and managed via PRO-Core's web-based administration systems. Satisfaction survey data will also be entered into the PRO-Core database via web-based administration. Abstracted medical record data will be entered into a PRO-Core study-specific database. PRO-Core employs a secure enterprise-level Oracle database managed by the ITS Research Computing group at UNC, and web servers are hosted by the UNC Center for Bioinformatics. Data transmitted between the server and end-users are encrypted using SSL, and all databases are encrypted.

CHAI Core and/or TS-PRO study team member(s) trained in qualitative interview will conduct all semi-structured interviews with patient and caregiver participants. Each interview will be audio recorded digitally and transcribed verbatim. The interview recordings and transcripts will be stored in a study-specific password-protected folder.

The Principal Investigator will provide continuous monitoring of patient safety in this trial with periodic reporting to the Data and Safety Monitoring Committee (DSMC) as required.

Meetings/teleconferences will be held at a frequency dependent on study accrual, and in consultation with the study Biostatistician. At these meetings, the research team will discuss all issues relevant to study progress, including enrollment, safety, regulatory, data collection, etc. and the team will produce summaries or minutes of these meetings. These summaries will be available for inspection when requested by any of the regulatory bodies charged with the safety of human subjects and the integrity of data including, but not limited to, the oversight (Office of Human Research Ethics (OHRE) Biomedical IRB, the Oncology Protocol Review Committee (PRC) or the North Carolina TraCS Institute Data and Safety Monitoring Board (DSMB).

8.0 STUDY MANAGEMENT

8.1 Institutional Review Board (IRB) Approval and Consent

It is expected that the IRB will have the proper representation and function in accordance with federally mandated regulations. The IRB should approve the consent form and protocol.

In obtaining and documenting informed consent, the investigator should comply with the applicable regulatory requirement(s), and should adhere to Good Clinical Practice (GCP) and to ethical principles that have their origin in the Declaration of Helsinki.

Before recruitment and enrollment onto this study, the patient will be given a full explanation of the study and will be given the opportunity to review the consent form. Each consent form must include all the relevant elements currently required by the FDA Regulations and local or state regulations. Once this essential information has been provided to the patient and the investigator is assured that the patient understands the implications of participating in the study, the patient will be asked to give consent to participate in the study by signing an IRB-approved consent form.

Prior to a patient's participation in the trial, the written informed consent form should be signed and personally dated by the patient and by the person who conducted the informed consent discussion.

